10.6 Study Monitoring Committees

10.6.1 Data Monitoring Committee

The DMC consists of specialists within relevant therapeutic areas. The DMC ensures that the ethical principles are observed and monitors the safety of the patients. The DMC will be

informed to what extent the data and analyses provided to them have been quality controlled. Members of the DMC will not be involved in other study-related tasks. The DMC procedures are described in the *Data Monitoring Committee Charter*.

11 Data Handling and Record Keeping

11.1 Data Collection

11.1.1 Electronic Case Report Forms (eCRFs)

eCRFs will be used to collect all the data related to the study, except the external data described in section 11.1.3.

The eCRFs use third party software (Rave®) to capture data via an on-line system on a computer. Data related to the study will be recorded electronically in a central database over encrypted lines, and all entries and modifications to the data will be logged in an audit trail. Access to the system will only be granted after appropriate and documented training. Written instructions for using the system will be provided along with the training.

Electronic signatures will be used where signatures are required on pages and/or visits. Automated data entry checks will be implemented where appropriate; other data will be reviewed and evaluated for accuracy by the CRA. All entries, corrections, and changes must be made by the investigator or a delegate.

11.1.2 Patient Binders

11.1.2.1 Use of Patient Binders

Lundbeck will provide a *Patient Binder* for each patient. The *Patient Binder* contains different types of source documents, organised by visit and type. A ballpoint pen with waterproof ink must be used to enter information in the *Patient Binder*.

Data from the source documents should be recorded in the eCRF within 3 days of the patient visit.

11.1.2.2 Rating Scales and Caregiver Outcome

The *Patient Binder* contains paper versions of the rating scales and caregiver outcomes. They will be completed by the rater(s) and caregiver, respectively. The data will be transcribed to the *Scoring Sheets* in the eCRF by the investigator or a delegate.

The rater(s) must verify that all the entries in the *Scale* Section are accurate and correct by signing and dating the relevant pages.

Caregiver's response cannot be corrected by the site staff.

11.1.2.3 Serious Adverse Event Fallback Forms

Serious Adverse Event Fallback Forms must be used when the eCRF cannot be accessed.

11.1.3 External Data

All electronic data will be transferred using a secure method accepted by Lundbeck.

The clinical safety laboratory results will be transferred by Quintiles Laboratories.

ECG results will be transferred by Quintiles Cardiac Safety Services.

11.2 Retention of Study Documents at the Site

11.2.1 eCRF Data

If a site closes before the study has been completed, the investigator will continue to have read-only access to the eCRF. If a site closes after the study has been completed, the investigator will no longer have read access to the eCRF. Instead, each site will be provided with a CD-ROM containing the data related to the site (including eCRF data, queries, and the audit trail). As a CD-ROM is not considered a durable medium and may therefore not be readable for the full retention period (for example, 15 years [if required by the applicable regulatory requirements]), it is possible for the investigator to request a new CD-ROM with the data related to the site.

11.2.2 Other Study Documents

The investigator must keep the investigator's set of documents in the investigator TMF for at least 15 years after the *Clinical Study Report* has been approved or in accordance with national requirements, whichever is longer.

The Investigator will be requested to store the investigator TMF in a sealed archive box at an off site storage facility to ensure safe storage and easy retrieval of the study documents for the entire retention period. A study-specific binder will remain at the site after the other study-specific documents have been shipped for off-site storage. This binder is considered part of the investigator TMF and must be kept in a secure place by the site for the required period of time. The binder must contain, at a minimum, the following documents: a copy of the *Investigator TMF Index*, a certified copy of the *Patient Identification Code List*, and a *Retrieval Form*.

Lundbeck will notify the investigator in writing when the required storage period has expired and when the documents may be destroyed according to regulations.

12 Monitoring Procedures

Prior to including patients in the study, the investigator must sign a source data agreement that identifies the source documents (original documents, data, and records) at the site.

During the study, the CRA will visit the site to ensure that the protocol is being adhered to and that all issues are being recorded, to perform source data verification, and to monitor IMP accountability. The visit intervals will depend on the outcome of the remote monitoring of the eCRFs, the site's recruitment rate, and the compliance of the site to the protocol and *Good Clinical Practice*.³ In addition, the CRA will be available for discussions by telephone.

Source data verification requires that the CRA be given direct access to all the source documents. Direct access includes permission to examine, analyse, verify, and reproduce any records and reports that are important for the evaluation of the study.

For all other data in the eCRFs, it must be possible to verify these against source documents.

13 Audits and Inspections

Authorised personnel from Global Clinical Quality Assurance at Lundbeck and quality assurance personnel from business partners may audit the study at any time to assess compliance with the protocol and the principles of *Good Clinical Practice*³ and all other relevant regulations.

The patients must be informed that authorised personnel from Lundbeck may wish to review their medical records. The investigator must be aware and the patients must be informed that representatives from regulatory authorities may also wish to inspect source data, such as medical records.

The investigator must notify Lundbeck, without delay, of an announced inspection by a regulatory authority.

During audits and inspections, the investigator must permit direct access to all the source documents, including medical records and other documents pertinent to the study.

During audits and inspections, the auditors and inspectors may copy relevant parts of medical records. No personal identification apart from the screening or randomisation number will appear on these copies.

Patient data will not be disclosed to unauthorised third parties, and patient confidentiality will be maintained at all times.

14 Protocol Compliance

Deviations from the protocol must not occur.

Lundbeck has a "no-waiver" policy, which means that permission will not be given to deviate from the protocol.

If deviations occur, the investigator must inform the CRA and they must review, discuss, and document the implications of the deviation.

15 Study Termination

Lundbeck or a pertinent regulatory authority may terminate the study or part of the study at any time. The reasons for such action may include, but are not limited to:

- safety concerns
- proven lack of efficacy of the IMP in other studies

If the study is terminated or suspended, the investigator must promptly inform the patients and ensure appropriate therapy and follow-up. Furthermore, the investigator and/or sponsor must promptly inform the IECs and IRBs and provide a detailed written explanation. The pertinent regulatory authorities must be informed in accordance with national regulations.

If the risk/benefit analysis changes after the termination of the study, the new evaluation must be provided to the IECs and IRBs if it will have an impact on the planned follow-up of the patients who participated in the study. If so, the actions needed to protect the patients must be described.

16 Statistical Methodology

16.1 Responsibilities

The Department of Biostatistics, H. Lundbeck A/S, will perform the statistical analyses described below.

16.2 Analysis Sets

The following analysis sets will be used to analyse and present data:

- *all-patients-treated set* (APTS) all patients who took at least one dose of IMP in the open label treatment period (initial 28-week period).
- *all-patients-treated set 2* (APTS2) all patients who took at least one dose of both IMP and memantine in the open-label treatment period with memantine (substudy).

Each patient will be classified according to this definition at a Classification Meeting held after all the data have been entered in the study database and verified.

All descriptive statistics and statistical analyses in the open-label treatment period (initial 28week period) will be based on the APTS, and all analyses in the open-label treatment period with memantine (substudy) will be based on APTS2. Listings will be based on all patients entering the treatment period.

16.3 Descriptive Statistics

In general, summary statistics (n, arithmetic mean, standard deviation, median, lower and upper quartiles, minimum and maximum values) will be presented for continuous variables and counts and percentages will be presented for categorical variables.

Descriptive statistics will be presented for each treatment period separately.

Descriptive statistics for efficacy assessments (MMSE, ADAS-Cog, ADCS-ADL₂₃, ADCS-CGIC and NPI), Dependence scale, RUD Lite, and EQ-5D-3L will be presented by visit leadin study, and treatment group in the lead-in study and in total. For the open-label treatment period (initial 28-week period), data will be presented using data from both the lead-in study and the open-label treatment period (initial 28-week period).

If relevant, individual patient profile plots will be generated for selected variables, using data from both the lead-in study and the extension study.

16.4 Patient Disposition

Patient disposition and reason for withdrawal will be presented by treatment period.

Patient disposition will be summarised by lead-in study, and by treatment group in the lead-in study and in total and include the number of patients who completed and the number of patients who withdrew from the study.

The number of patients who withdraw from the study and primary reason for withdrawal as well as all reasons for withdrawal will be summarised by lead-in study, and treatment group in the lead-in study and in total.

Kaplan-Meier time to withdrawal plots in the open-label treatment period (initial 28-week period) will be generated by lead-in study, and treatment group in the lead-in study and in total.

16.5 Demographics and Other Baseline Characteristics

Demographics (sex, age, race) based on APTS and APTS2 will be summarised by treatment group (placebo or idalopirdine all doses pooled) in the lead-in study and in total.

16.6 Recent and Concomitant Medication

Recent and concomitant medication in each treatment period will be summarised by anatomical therapeutic chemical (ATC) code and generic drug name by treatment group (placebo or idalopirdine all doses pooled) in the lead-in study and in total.

16.7 Exposure

Exposure in each treatment period will be calculated per patient and summarised by treatment group (placebo or idalopirdine all doses pooled) in the lead-in study and in total.

Number and percentage of patients with dose reduction of IMP to 30 mg/day in the open-label treatment period (initial 28-week period) will be calculated by treatment group (placebo or idalopirdine all doses pooled) in the lead-in study and in total.

16.8 Efficacy Analyses

On an exploratory basis, changes from baseline in in the open-label treatment period (initial 28-week period) of ADAS-Cog total score, ADCS-ADL23 total score, NPI total score, NPI individual items, EQ-5D-3L utility score, and EQ-5D-3L VAS score will be analysed using a restricted maximum likelihood (REML)-based mixed model for repeated measures (MMRM) approach. Baseline will be defined as the baseline in the lead-in study. The analyses will be performed by lead-in study. The model for the lead-in studies 14861A and 14862A will include the fixed categorical effects of treatment group in the lead-in study, country, visit, treatment-by-visit interaction, MMSE-stratum (<19, \geq 19), and MMSE-stratum-by-visit interaction. In all analyses, an unstructured (co)variance structure will be used to model the within-patient errors. The Kenward-Roger approximation will be used to estimate denominator degrees of freedom.

ADCS-CGIC will be analysed using the same methodology, using the scores at each visit and the ADCS-CGIC score at baseline in the lead-in study as baseline.

16.9 Safety Analyses

Safety tables will be presented for each treatment period separately by treatment group (placebo or idalopirdine all doses pooled) in the lead-in study, and in total.

16.9.1 Analysis of Adverse Events

Adverse events will be classified according to when the adverse event started:

• *treatment-emergent adverse event* (TEAE) – an adverse event that starts on or after the date of first dose of IMP in the extension study and prior to the last protocol-specified contact with that patient. TEAEs may be divided into study periods (these will be defined in the Statistical Analysis Plan).

Adverse events, sorted by system organ class (SOC) and preferred term, will be summarised by treatment group in the lead-in study and in total.

If relevant, incidence and prevalence in the lead-in study and in the open-label treatment period (initial 28-week period) for selected preferred terms will be presented by treatment group in the lead-in study.

16.9.2 Analysis of Other Safety Endpoints

Clinical safety laboratory tests, vital signs, weight and ECG parameters will be summarised by visit and last post baseline assessment in the treatment period. For the open-label treatment period (initial 28-week period), the summaries will be presented using data from both the lead-in study and the open-label treatment period (initial 28-week period).

Potentially clinically significant (PCS) values will be flagged and summarised.

If relevant, individual patient profile plots will be generated for selected parameters, using data from both the lead-in study and the extension study.

C-SSRS will be summarised by visit. For the open-label treatment period (initial 28-week period), the summaries will be presented using data from both the lead-in study and the open-label treatment period (initial 28-week period).

16.9.3 Analysis of Liver Tests

In addition to the standard summary of clinical safety laboratory tests, the incidences of

- ALT/AST > 1x, 1.5x, 2x, 3x, 5x, 10x, 20x ULN
- TBL > 1x, 1.5x, 2x ULN
- AP > 1.5x, 2x ULN
- ALT/AST > 3xULN and TBL > 2xULN
- ALT/AST > 3xULN and TBL > 2xULN and AP \leq 1.5xULN
- ALT/AST > 3xULN and (TBL > 2xULN or INR > 1.5xULN) and AP \leq 1.5xULN

will be produced.

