5.4 Withdrawal Criteria

A patient must be withdrawn from the study if:

- the patient and/or his or her legal representative withdraws his or her consent (defined as a patient and/or his or her legal representative who explicitly takes back his or her consent); section 8.3 states how the patient's data will be handled.
- the investigator considers it, for safety and/or study compliance reasons, in the best interests of the patient that he or she be withdrawn.
- the patient has a serum ALT or AST value >8 times the upper limit of the reference range.* (Not applicable for the Czech Republic)
- the patient has a serum ALT or AST value >5 times the upper limit of the reference range that is confirmed by testing within 5 days. (Applicable for the Czech Republic only)
- the patient has a serum ALT or AST value >3 times the upper limit of the reference range and a serum total bilirubin value >2 times the upper limit of the reference range.*
- the patient has a serum ALT or AST value >3 times the upper limit of the reference range and an international normalised ratio of prothrombin time (INR) more than 1.5.*
- the patient has a serum ALT or AST value >5 times the upper limit of the reference range for >2 weeks.* (Not applicable for the Czech Republic)
- the patient has a serum ALT or AST value >3 times the upper limit of the reference range with the appearance of fatigue, nauseas, vomiting, right upper quadrant pain or tenderness, fever, rash, and/or eosinophilia (>5%).*
- the patient has a QTcF interval >500 ms that is confirmed with an ECG taken at a visit <2 weeks later.
- the patient attempts suicide or is at significant risk of suicide (either in the opinion of the investigator or defined as a "yes" to suicidal ideation questions 4 or 5 or answering "yes" to suicidal behaviour on the C-SSRS during the study).

- the patient is lost to follow-up (defined as a patient who fails to comply with scheduled study visits or contact, who has not actively withdrawn from the study, and for whom no alternative contact information is available [this implies that at least two attempts have been made to contact the patient]).
 - * in accordance with the FDA "Guidance for Industry Drug-Induced Liver Injury: Premarketing Clinical Evaluation"⁵

Patients who withdraw will not be replaced.

6 Investigational Medicinal Products

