11.3.3 Evaluation of Potential Drug-induced Liver Injury (DILI)

Signals of DILI post-Baseline II for the open label treatment period and post Baseline III for the open label treatment period with memantine will be assessed according to the FDA guideline¹, as well as by using additional criteria, as described below:

The number and percentage of patients post-Baseline II/Baseline III in the categories below for AST/ALT, and AST and ALT separately will be summarised:

Version: 1.0

- ULN < value ≤ 1.5 xULN
- $1.5xULN < value \le 2xULN$
- $2xULN < value \le 3xULN$
- $3xULN < value \le 5xULN$
- $5xULN < value \le 10xULN$
- $10xULN < value \le 20xULN$

LU Study Number: 14861B Trial Site Number: Study Level Pluto ID: CLI 00933680

Status: Final

• 20xULN < value

The number and percentage of patients post-Baseline II/Baseline III in the categories below for ALP and Bilirubin will be summarised:

- ULN<value ≤1.5xULN
- 1.5xULN< value <2xULN
- 2xULN< value ≤3xULN
- value >3xULN

In the summaries, each patient should be counted only once using the worst post-Baseline II/Baseline III assessment.

The cumulative number and percentage of patients post-baseline in the categories will also be summarised for each treatment period.

Number and percentage of patients fulfilling the joint criteria below post-baseline II/Baseline III will be summarised:

- (PEAK AST OR PEAK ALT>3xULN) AND PEAK BILI>2xULN AND PEAK ALP>1.5xULN
- (PEAK AST OR PEAK ALT>3xULN) AND PEAK BILI>2xULN AND PEAK ALP<1.5xULN
- PEAK GGT>200 (IU/L) without (PEAK AST OR PEAK ALT OR PEAK ALP>2xULN)
- Number and percentage of patients with a post-Baseline II /Baseline III value ≥5% for Beosinophils/leukocytes (ESOLE) will be summarised.

Evaluation of potential Drug-Induced Serious Hepatotoxicity (eDISH) will also be done by plots. Scatter plots of peak ALT/AST versus peak BILI in the treatment period (note that this means that the peak ALT/AST and the peak BILI may not occur at the same assessment timepoint). The values will be normalised by the ULN (unit xULN) and the X and Y-axes will be on log scale. The plot will include a reference line for ALT/AST values >3xULN, and a reference line for BILI values>2xULN. Four quadrants are defined by the reference lines, where the right upper quadrant being the most specific indicator for a drug's potential for causing serious liver injury (Hy's law quadrant). The plot will include number of patients in each quadrant.

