Plasma concentrations of idalopirdine and memantine will be summarised descriptively for the APTS2 in the open-label treatment period with memantine.

13 Health Economic Analyses

The health economic assessments conducted during the open-label treatment period (RUD Lite, EQ-5D-3L and Dependence scale) in the open-label will be summarised by lead-in study. For the open label treatment period, absolute scores, change from Baseline I scores, and change from Baseline II will be summarised by visit week. The summaries of absolute scores and change from Baseline I scores will include data from the lead-in study and the open-label treatment period.

For the open label treatment period with memantine, absolute score and change from Baseline III in MMSE total score will be summarised by visit week.

14 Interim Analyses

No interim analyses planned.

Page 23 of 48 Trial Site Number: Study Level

LU Study Number: 14861B Pluto ID: CLI_00933680 Status: Final

Version: 1.0

15 Sample Size Considerations

Open-label treatment period:

The study will include eligible patients who have completed Visit 7 (Completion Visit) of the lead-in studies. Assuming a completion rate of 85% and that approximately 85% of these are eligible and complete the extension study, this results in a total of approximately $(3x310 + 3x280) \times 85\% \times 85\% \approx 1280$ patients completing this study.

Open-label treatment period with memantine (sub-study):

With a sample size of n=100 the upper 1-sided 90% confidence limit for 0 to 10 AEs observed is:

Number of AEs observed	0	1	2	3	4	5	10
Upper 1-sided CI for AE incidence	2.3%	3.9%	5.3%	6.6%	7.9%	9.1%	15.0%

This is regarded as sufficient accuracy for evaluating safety and tolerability.

16 Data and Analysis Standards and Statistical Software

The data will be collected and analysed in accordance with the Lundbeck standards specified in Lundbeck SDTM, Version 3.1.2 or later, SADs, Version 5.1 or later, and TGML, Version 7.0 or later.

The statistical software used will be SAS®, Version 9.4 or later.

17 Changes to Analyses Specified in the Protocol

C-SSRS will be summarized as worst case per treatment period rather than worst case per visit. However, all C-SSRS results for the study will be listed for those patients that experience any suicidal ideation or behaviour.

18 Details on Data Handling

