Appendix IV PCS Criteria

LU Study Number: 14861B Trial Site Number: Study Level Pluto ID: CLI_00933680

PCS Criteria

Table 1 PCS Criteria for Clinical Safety Laboratory Tests

CDISC term	Test (units)	PCS Low	PCS High
Liver			
AST	S-aspartate aminotransferase (IU/L)		$\geq 3 \times ULN$
ALT	S-alanine aminotransferase (IU/L)		\geq 3 × ULN
BILI	S-bilirubin (μmol/L)		≥ 34
BILDIR	S-direct bilirubin (µmol/L)		≥ 12
ALP	S-alkaline phosphatase (IU/L)		$\geq 3 \times ULN$
GGT	S-gamma glutamyl transferase (IU/L)		≥ 200
Kidney			
CREAT	S-creatinine (µmol/L)		$\geq 1.5 \times ULN$
BUN	B-urea nitrogen (mmol/L)		≥ 11
Electrolytes			
SODIUM	S-sodium (mmol/L)	≤ 125	≥ 155
K	S-potassium (mmol/L)	≤ 3.0	≥ 6.0
CA	S-calcium (mmol/L)	≤ 1.8	≥ 3.0
BICARB	S-bicarbonate (mmol/L)	≤ 12	≥ 38
Endocrine/Meta	bolic		
GLUC	Serum glucose (mmol/L)	≤ 3.9	≥ 11.1
GLUC	Serum glucose, fasting (mmol/L)	≤ 3.5	≥ 7.0
TSH	S-thyrotropin (mIU/L)	≤ 0.3	≥ 5.5
ALB	Albumin (g/L)	≤ 27	
Lipids			
CHOL	S-cholesterol (mmol/L)		≥ 7.8
CHOL	S-Cholesterol, fasting (mmol/L)		≥ 6.2
TRIG	Triglycerides (mmol/L)		≥ 5.65
TRIG	Triglycerides, fasting (mmol/L)		≥ 4.2
Haematology/Co	pagulation		
INR	P-INR (Prothrombin ratio)		≥ 2.0
PLAT	B-thrombocytes platelet count (×10E9/L)	≤ 75	≥ 600
HGB	B-haemoglobin (g/dL)	≤ 9.5 (women) ≤ 11.5 (men)	≥ 16.5 (women) ≥ 18.5 (men)
RBC	B-erythrocytes (×10E12/L)	≤ 3.5 (women) ≤ 3.8 (men)	\geq 6.0 (women) \geq 7.0 (men)
WBC	B-Leukocytes (×10E9/L)	\leq 2.8	≥ 16
NEUTLE	B-Neutrophils/leukocytes (%)	≤ 20	≥ 85
EOSLE	B-eosinophils/leukocytes (%)		≥ 10

Page 47 of 48

LU Study Number: 14861B Pluto ID: CLI_00933680

Status: Final

Version: 1.0

CDISC term	Test (units)	PCS Low	PCS High
BASOLE	B-basophils/leukocytes (%)		≥ 10
LYMLE	B-Lymphocytes/leukocytes (%)	≤ 10	≥ 75
MONOLE	B-Monocytes /leukocytes (%)		≥ 15
Infection			
CRP	S-C-reactive protein (mg/L)		≥ 25
Urine			
GLUC	U-Glucose		Increase≥2
KETONES	U-Ketones		Increase≥2
OCCBLD	U-Occult Blood		Increase≥2

Table 2 PCS Criteria for Vital Signs and Weight

CDISC term	Variable (units)	PCS Criterion Low	PCS Criterion High
WEIGHT	Weight (kg)	Decrease ≥ 7%	Increase ≥ 7%
BMI	Body mass index (kg/m2)	Decrease $\geq 7\%$	Increase $\geq 7\%$
DIABP	Supine diastolic blood pressure (mmHg)	\leq 50 and decrease \geq 15	≥ 105 and increase ≥ 15
SYSBP	Supine systolic blood pressure (mmHg)	\leq 90 and decrease \geq 20	≥ 180 and increase ≥ 20
PULSE	Pulse rate supine/sitting/unknown (bpm)	\leq 50 and decrease \geq 15	\geq 120 and increase \geq 15

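### The protocol's joint liver row sets INR at 1.5 times ULN, its withdrawal criterion uses an absolute 1.5, and the SAP's joint liver rows have no INR term

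*Protocol*

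**What the plan says.** Protocol 5.4 lists the reasons for which a patient must be withdrawn. One is ALT or AST above 3xULN together with "an international normalised ratio of prothrombin time (INR) more than 1.5". It is starred as following the FDA guidance on drug-induced liver injury. The enzyme and bilirubin limits in that list are multiples of the upper limit; the INR limit is a plain number. The criterion has no AP condition.

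Protocol 16.9.3 lists the liver incidences to be produced. The last row is "ALT/AST > 3xULN and (TBL > 2xULN or INR > 1.5xULN) and AP" at or below 1.5xULN. Here INR too is a multiple of the upper limit.

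SAP 11.3.3 gives its own joint criteria. The one nearest to the protocol row is "PEAK AST OR PEAK ALT>3xULN) AND PEAK BILI>2xULN AND PEAK ALP<1.5xULN", which uses bilirubin only. No joint criterion in that section mentions INR. In the SAP's criteria, INR appears only in Appendix IV, Table 1, as a stand-alone flag for potentially clinically significant values at 2.0 or more. SAP section 17, on changes from the protocol, records only that "C-SSRS will be summarized as worst case per treatment period rather than worst case per visit", plus a related note on listings.

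**The concern.** One protocol uses two scales for the same test in combination with the same transaminase limit, and gives no reason. If the upper limit for INR is above 1.0, the tabulation limit is the higher of the two. A patient can then be withdrawn under the INR criterion and not be counted in the only planned row that combines transaminases with INR. The SAP goes further and drops INR from the joint count without saying so.

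Safety is the primary objective, and liver tests are the known signal. Protocol 1.1.3.3 reports 13 patients with AST or ALT above 2xULN in the phase II study, all on idalopirdine, with the mechanism unknown. Clotting also has some relevance: protocol 1.1.2 notes longer clotting time in rats at high exposure, and SAP 11.1.11 makes haemorrhages an event of special interest. At stake is whether the report shows how many patients had raised transaminases and a raised INR at the limit that the protocol itself acts on.

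**Working it through.** **Inputs**

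- Withdrawal criterion (protocol 5.4): ALT or AST > 3xULN and INR > 1.5.
- Protocol row (16.9.3): ALT/AST > 3xULN and (TBL > 2xULN or INR > 1.5xULN) and AP ≤ 1.5xULN.
- SAP joint rows (11.3.3): transaminases > 3xULN and bilirubin > 2xULN, split by ALP above or below 1.5xULN.
- SAP INR flag (Appendix IV, Table 1): INR ≥ 2.0.
- INR upper limit: not given. Assumed range 1.0 to 1.3.

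**Step 1: the two INR limits.** Row limit = 1.5 × ULN. Uncounted band = 1.5 × ULN − 1.5.

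**Step 2: test patients.** Take ALT 4xULN, TBL 1xULN, AP 1xULN and INR of 1.6, 1.7 or 1.9. All three meet 5.4, because 4 > 3 and INR > 1.5. The last three columns show whether the protocol row counts them.

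| Assumed INR ULN | Row limit | Band width | INR 1.6 | INR 1.7 | INR 1.9 |
|---|---|---|---|---|---|
| 1.0 | 1.50 | 0 | yes | yes | yes |
| 1.1 | 1.65 | 0.15 | no | yes | yes |
| 1.2 | 1.80 | 0.30 | no | no | yes |
| 1.3 | 1.95 | 0.45 | no | no | no |

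With TBL > 2xULN and AP ≤ 1.5xULN a patient is counted whatever the INR, so the gap concerns only TBL ≤ 2xULN.

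**Step 3: the SAP.** With TBL 1xULN none of the three patients enters an SAP joint row, at any ULN. None reaches the INR flag either, since 1.9 < 2.0. Over the assumed range the whole band lies below the flag: its upper end is 1.95, and 1.5 × ULN reaches 2.0 only at ULN = 2.0 / 1.5 = 1.33. The SAP gap is also wider than the protocol's band, because any patient with TBL ≤ 2xULN is outside the joint rows however high the INR.

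**Step 4: where these patients do appear.** ALT 4xULN falls in the category above 3xULN up to 5xULN (SAP 11.3.3). The withdrawal and its reasons are listed (SAP 6.2), as are any adverse events leading to withdrawal (SAP 11.1.9). The liver listing and individual plots in SAP 11.3.3 cover ALT, AST, bilirubin, ALP, GGT and eosinophils, but not INR. No planned summary joins the two findings.

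**Step 5: after alignment.** With INR > 1.5 in the row, all three test patients are counted at every ULN. The same patients with AP 1.8xULN meet 5.4 and remain outside the row, because of its AP condition.

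**The case against.** The strongest objection is that the mismatch sits in a row that the SAP does not carry. Protocol 16.12 leaves the detail of the analyses to the SAP, whose joint rows have no INR term, so editing the protocol threshold alone would change no SAP table. This is right, and it is why the SAP has to be part of the correction. It does not make the mismatch harmless: restoring the protocol's row as written would bring in the mismatched limit.

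A second objection is that a withdrawal rule and a tabulation row need not coincide. The row merges bilirubin with INR and adds an AP condition, so it was never a count of patients meeting 5.4. This also stands. The case for alignment is only that the two INR scales differ without explanation.

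Third, SAP 11.3.3 says that liver signals will be assessed according to the same FDA guidance that 5.4 cites, which might be taken to cover INR. The criteria it then sets out contain no INR term, so no such table is specified.

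Two stronger readings are tempting. A reader might infer that the reported incidence of liver injury would be too low, or that one omitted case would change the conclusion. The documents support neither. The row would report correctly what it defines, safety is summarised descriptively with no decision rule, and the affected patients appear in other outputs. The phase II summary found no treatment difference in bilirubin above ULN and reports no INR finding, so nothing shows that any patient will fall in the band.

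**Conclusion.** The inconsistency is real, and the gap is one of joint reporting. For any INR ULN above 1.0, a patient with ALT or AST > 3xULN, TBL ≤ 2xULN, AP ≤ 1.5xULN and INR above 1.5 but not above 1.5xULN meets 5.4 and is absent from the protocol's joint row. The SAP joint rows omit such a patient at any ULN, and section 17 does not disclose that the INR term was dropped.

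The width of the protocol's band rests wholly on an assumed ULN: 0 at 1.0, rising to 0.45 INR units at 1.3. The number of patients affected cannot be estimated from the documents. The point deserves correction because it concerns the drug's known safety signal and is cheap to put right. It implies no view on which INR limit is clinically appropriate.

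**What to change.** Reconcile protocol 5.4, protocol 16.9.3 and SAP 11.3.3. As a tabulation matter only, put the same joint row into protocol 16.9.3 and SAP 11.3.3:

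- ALT/AST > 3xULN and (TBL > 2xULN or INR > 1.5, on the absolute scale of 5.4) and AP ≤ 1.5xULN.

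The version with INR > 1.5xULN can stay as an extra row. A footnote should say that the row does not count patients who meet 5.4 but have AP > 1.5xULN. If the sponsor prefers not to tabulate INR jointly, SAP section 17 should list that as a change and give the reason.

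The cost is one added SAP row with its code and one changed threshold in the protocol's analysis text. INR is already in the laboratory panel (protocol Panel 5), so no new data are needed and patient care is unaffected. The reported joint count may become slightly less favourable.
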